20.0 STATISTICAL CONSIDERATIONS

20.1 Study Design

This is a Phase II trial of seven weeks RT+cetuximab for head and neck cancer in patients with good prognoses to determine if this treatment will be at least as effective as, but less toxic than, standard therapy. A total of 43 patients will be enrolled in order to obtain 36 patients that complete radiation treatment and have both biopsies taken. Thus, both the clinical primary endpoints and scientific secondary endpoints can be analyzed, as EGFR tumor information is useful for determining potential mechanisms of resistance to cetuximab. Based on the experience of UMCC 9921 and UMCC 2-21, accrual is expected to average one patient per month. To be considered evaluable, a patient must complete the full course of radiation/cetuximab. If radiation and/or cetuximab was stopped or modified due to toxicity, the patient is still evaluable. Inevaluable patients will be replaced.

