20.2 Early Stopping Rules for Toxicity or Lack of Efficacy

In UMCC 9921 and UMCC 2-21, 2/32=6% of patients similar to those who will be treated in the current trial did not achieve tumor control. An early stopping rule will only be feasible for the identification of probability of treatment failure much higher than that. Table 1 describes the stopping rule for failure to control, which was derived using the method due to Thall, Simon and Estey [31], implemented in M.D. Anderson program multc98. **Failure is defined as local-regional recurrence or metastasis, but not second primary cancer, nor microscopic disease found in elective neck dissection, nor PET findings without correlative clinical evidence of disease persistence or recurrence.** For each number of patients enrolled, if *at least* as many failures as stated occurs (e.g., 2/5), accrual will be stopped. The rule was constructed to stop the trial if the probability that the failure rate of the experimental therapy exceeded 0.1625 (0.1 more than the historical rate) is at least 0.75.

# Patients	# Failures
5	2
10	3
15	4
20	5
25	6
30	7

Table 1 Stopping rule for failure to control tumor

Because the trial will only be stopped early for failure, and the stopping rule does not constitute an interim analysis, there will be no adjustment to the p-values of the analyses in Section 20.4.

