20.4 Justification of Design

20.4.1 Early stopping rule for tumor control

The operating characteristics of the stopping rule were analyzed using the simulation tool in multc98. The probability the trial will be stopped early, and the distribution of the expected sample sizes, was calculated under the

assumption that the true probability of failure varied from 0.06 to 0.6. The operating characteristics are displayed in Table 2. For instance, if the true probability of failure equaled 0.2, 0.59 of the trials stopped early, 50% of the trials stopped after accruing 20 or fewer patients, and 25% of the trials stopped after accruing five or fewer patients.

True P(Failure)	P(Stop Early)	Sample Size Percentiles				
		10	25	50	75	90
0.06	0.05	35	35	35	35	35
0.2	0.59	5	5	20	35	35
0.3	0.91	5	5	10	15	30
0.4	0.99	5	5	5	10	15
0.5	0.99	5	5	5	5	19

Table 2 Operating characteristics of stopping rule for treatment failure

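### The tumor-failure stopping rule has no look after patient 30 although 43 are to be enrolled, and its operating characteristics are computed for 35 patients with outcomes known at once

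*Combined protocol and SAP*

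**What the plan says.** Section 20.1 sets the size: "A total of 43 patients will be enrolled in order to obtain 36 patients that complete radiation treatment and have both biopsies taken". It adds that "accrual is expected to average one patient per month". A patient is evaluable after completing the course of radiation and cetuximab; a second biopsy is not part of that definition.

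Section 20.2 gives the rule: "For each number of patients enrolled, if *at least* as many failures as stated occurs (e.g., 2/5), accrual will be stopped". The boundaries under "Table 1 Stopping rule for failure to control tumor" are 2 failures in 5, 3 in 10, 4 in 15, 5 in 20, 6 in 25 and 7 in 30. On the criterion, the section says: "The rule was constructed to stop the trial if the probability that the failure rate of the experimental therapy exceeded 0.1625", with 0.75 as the probability that triggers a stop. The historical reference is that "2/32=6% of patients similar to those who will be treated in the current trial did not achieve tumor control". Failure means local-regional recurrence or metastasis. No time window and no minimum follow-up per look are given.

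Section 20.4.1 reports simulated performance in "Table 2 Operating characteristics of stopping rule for treatment failure". The stopping probabilities are 0.05, 0.59, 0.91, 0.99 and 0.99 at true failure rates of 0.06, 0.2, 0.3, 0.4 and 0.5. The largest sample-size percentile shown is 35.

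**The concern.** The rule counts enrolled patients and acts by closing accrual, so it should run for as long as patients are being enrolled. It ends at 30 of 43, and no number of failures after that triggers anything. Section 2.0 relies on strict stopping rules to ensure that the reduced-intensity regimen does not increase tumor failures, and a rule that lapses before accrual ends only partly delivers that.

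The table meant to show how the rule performs does not describe the planned trial either. Its maximum of 35 matches no sample size in Section 20.1. It also takes no account of the delay between enrolment and a recurrence, while the primary recurrence index in Section 20.3.1.1 runs to two years after treatment. A safety board reading 0.91 at a failure rate of 0.30 would expect more protection than the rule gives when failures arrive late.

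**Working it through.** **Inputs from the documents.** Looks and boundaries: Table 1. Criterion: P(failure rate > 0.1625) at least 0.75 (Section 20.2). Enrolment 43, target 36, accrual one per month (Section 20.1). Radiotherapy over 7 weeks after a loading dose about a week earlier (Section 7.2), taken as 2 months.

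**Inputs that are assumptions.** The prior is not stated, and neither is the timing of failures. Both are varied below.

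**1. Patients beyond the last look.** 43 − 30 = 13, and 13/43 = 30%. If the rule were read as counting only the 36 target patients, 6/36 = 17%.

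**2. Reproduce Table 2.** Take d(x), the probability of x failures without having stopped. Convolve it with Binomial(5, p) between looks, and at each look remove the mass at or above the boundary. The removed mass sums to P(stop). Every enrolled patient's outcome is treated as known at each look.

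| True rate | Table 2 | Recomputed |
|---|---|---|
| 0.06 | 0.05 | 0.046 |
| 0.2 | 0.59 | 0.594 |
| 0.3 | 0.91 | 0.912 |
| 0.4 | 0.99 | 0.992 |
| 0.5 | 0.99 | 0.9997 |

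With a maximum of 35 the percentiles also match, except one. At 0.5 the cumulative stopping probability is 0.81 at 5 patients and 0.955 at 10, so the 90th percentile is 10. The table prints 19, which is not a look. Table 2 is therefore reproduced with immediate outcomes and a maximum of 35.

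**3. Effect of the maximum alone.** All looks end at 30, so moving the maximum from 35 to 43 changes no P(stop). Percentiles printed as 35 become 43, and expected enrolment at 0.2 goes from 21.0 to 24.3.

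**4. Extend the boundary.** With a Beta(a, b) prior, the rule stops at r failures in n if P(Beta(a + r, b + n − r) > 0.1625) ≥ 0.75. A Beta(0.125, 1.875) prior (mean 0.0625, weight 2) returns all six rows of Table 1. It then gives 8 in 35 (posterior 0.794; 0.653 with 7) and 9 in 40 (0.801; 0.672 with 8). Prior weights of 0.2, 0.5, 1, 2, 2.5 and 2.6 with the same mean all return Table 1 and the same two new rows.

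**5. Gain with immediate outcomes, maximum 43.** P(stop) goes from 0.046 to 0.046 at 0.06, from 0.594 to 0.641 at 0.2, from 0.912 to 0.948 at 0.3, and from 0.992 to 0.998 at 0.4. At 0.5 it is above 0.99 either way.

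**6. Gain with an outcome lag.** Patient i enrols at month i, ends treatment at month i + 2, and fails with probability p at a time uniform over H months after that. A look at n patients falls at month n and counts only failures that have already occurred. Results are from 200,000 simulated trials per cell, as current rule → extended rule.

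| Failures spread over | p = 0.06 | p = 0.20 | p = 0.30 |
|---|---|---|---|
| 24 months | 0.0001 → 0.0001 | 0.035 → 0.079 | 0.19 → 0.40 |
| 12 months | 0.0013 → 0.0014 | 0.17 → 0.24 | 0.54 → 0.70 |
| 6 months | 0.0042 → 0.0043 | 0.29 → 0.36 | 0.71 → 0.82 |

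**7. Enrolments spared.** At 0.30, mean enrolment falls from 39.8 to 38.7 (24 months), from 31.9 to 30.9 (12 months) and from 25.9 to 25.2 (6 months). With immediate outcomes the fall is about 0.2.

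**8. Share of failures visible.** By look 30 the expected share of all failures among 43 patients is Σ min(1, max(0, (30 − i − 2)/H))/43 over i = 1 to 30. For H = 24 this is (4 + 11.5)/43 = 36%. A further 30% surface between patients 30 and 43, and 34% after accrual closes. For H = 12 the share by look 30 is 50%, and for H = 6 it is 57%.

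**The case against.** Under Table 2's own assumption the missing looks add only 4 to 5 percentage points at 0.20 and 0.30. The rule only closes accrual, so a stop at 35 spares 8 enrolments and a stop at 40 spares 3. If 35 was the intended maximum, ending at 30 is coherent, because a look at 35 could stop nothing. Oversight also continues: Section 18.0 has the study committee meeting at least quarterly and an independent board reviewing quarterly. Section 20.2 itself says early stopping is feasible only for failure rates much above the historical one, and Section 20.4.2.1 disclaims a definitive efficacy test.

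Most of this stands and limits the size of the point. It does not close the gap, because the planned enrolment is 43 and Section 18.0 attaches no failure boundary to its reviews.

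Two stronger readings are tempting. A reader might infer that the rule ends just when most failures become visible, or that the missing looks are the most powerful ones. Both depend on failure timing that the documents do not give. Even in the slowest case above, only about 30% of failures surface between patient 30 and the end of accrual. With failures within 12 months or less, half or more are visible by look 30. A reader might also infer that the 35-versus-43 mismatch makes Table 2's stopping probabilities wrong. It does not; only the percentiles change.

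**Conclusion.** The point holds as a cheap improvement. That the rule lapses at patient 30 of 43, and that Table 2 uses a maximum found nowhere in Section 20.1, follow directly from the documents. The boundaries 8/35 and 9/40 rest on an assumed prior, but every prior weight tried that reproduces Table 1 gives them.

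The gain in stopping probability is small with immediate outcomes and larger with delay: 11 to 21 percentage points at a failure rate of 0.30 across the lags examined, with no material rise in false stops at 0.06. Those lag figures depend on the assumed accrual, treatment time and uniform failure times. The 24-month upper value is borrowed from the primary recurrence index, because Section 20.2 gives its own failures no window.

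At 0.20, the rate tested in Section 20.3.1.1, the extended rule still stops only 8% to 36% of trials under these lags. Two more looks therefore do not cure the larger limitation, which is that Table 2 assumes outcomes known at once and no follow-up per look is specified. The printed 19 is minor, possibly a misprint, and has no bearing on the design.

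**What to change.** - Add two rows to Table 1 by the existing criterion: 8 failures in 35 and 9 failures in 40. State the prior.
- State whether the rule counts enrolled or evaluable patients, and what minimum follow-up, if any, a patient needs to count at a look.
- Re-run Table 2 for a maximum of 43. With immediate outcomes and the added looks, P(stop) should come out near 0.05, 0.64, 0.95, >0.99 and >0.99 at 0.06, 0.2, 0.3, 0.4 and 0.5. Beside it, show a version with a stated accrual rate and failure-time assumption, including the 0.20 row.
- Check the 90th percentile in the 0.5 row; it computes to 10.

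The cost is two more counts, which can be made at the existing quarterly reviews, and one re-run of the stopping-rule program. The sample size and the final analysis do not change.

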20.3 Analysis Plan

20.3.1 Primary Objectives

20.3.1.1 *To confirm that reducing treatment intensity in non-smoking patients with HPV-related oropharyngeal cancer does not significantly increase the proportion of patients whose tumors recur, compared to our previous experience in similar patients receiving standard-intensity chemo-RT.*

The primary index of recurrence will be the proportion of patients who have local recurrence, distant metastases or second primaries (secondary analyses will be performed on each of these endpoints individually) within two years of the end of treatment. In the primary analysis, *null* hypothesis that the proportion of patients who fail is *greater* than 0.20 will be tested using an exact binomial test (at significance level $\alpha=0.20$). The proportion of patients who recur will be calculated, with a 95% exact binomial confidence interval.

20.3.1.2 *To compare the toxicity in patients receiving reduced intensity treatment to similar patients treated with 7 weeks of chemotherapy concurrent with RT ("standard therapy") in UMCC 2-21.*

Dysphagia and mucositis are measured on continuous scales; there are both observer and patient reports. The null hypothesis of no difference in dysphagia and mucositis at three, twelve and twenty-four months posttreatment between the reduced-intensity therapy versus UMCC 2-21 will be tested ($\alpha=0.20$) in a repeated measures analysis of covariance. In addition, the statistical significance of the difference between the current trial and UMCC 2-21 in the proportions of patients experiencing clinically significant (NCI CTCAE Grade 3 or worse) toxicities will be assessed using Fisher's exact test

(a=0.20).

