Despite the favorable prognosis associated with, HPV-positive tumors, this biologic marker has not yet been used to determine therapeutic management. We postulate that there are two subsets of HPV-positive SCCOP patients; those who are cured by current therapies but may be suffering unnecessary morbidity from over-treatment and those who are at higher risk for disease progression and require more aggressive therapies. In prior work, we have investigated tobacco use and the HPV-16 biomarker as variables that can differentiate patients to one of those two subgroups, thereby allowing clinicians to safely develop more selective therapies for subsets of HPV-positive SCCOP patients.

One hundred and twenty-four patients with newly diagnosed, stage III or IV SCCOP whose tumors were analyzed for HPV presence and type were included in this study. Patients were treated according to one of two consecutive treatment protocols at the University of Michigan. Of the 124 patients, one hundred two were HPV-positive (82.3%) and 22 (17.7%) were HPV negative. Thirty- two (32/102, 32.4%) had disease progression (DM, LR, or SP). Seventeen patients (17/124, 13.7%) developed DMs (12 HPV-positive; 5 HPV-negative), nine (9/124; 7.3%) developed LRs (5 HPVpositive; 4 HPV-negative), and 8 (8/124; 6.5%) developed SPs (5 HPV-positive; 3 HPV-negative). Of thirty-three HPV-positive never-tobacco users, only one patient had disease progression (DM) (1/32, 3%), and an additional patient had a second primary in the oral cavity. Approximately two- thirds (68%) of the 102 HPV-positive patients were former or current tobacco users. Of these 69 patients, 18 (26%) developed a total of 20 disease progression events. All of the 22 HPV-negative SCCOP patients were tobacco users at some time. Twelve of the 22 (55%) HPV-negative former or current tobacco users had disease progression events (five DMs, four LRs, and three SPs). Sixteen

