Taking into account the high local-regional control rates achieved in our oropharyngeal cancer patients after 7 weeks of concurrent chemo-RT, we hypothesize that additional gains in our efforts to reduce treatment sequelae may be achieved if we could safely reduce the intensity of therapy in those patients who are most likely to respond completely. A recent analysis of RTOG study comparing accelerated to standard fractionation concurrent with chemotherapy, found that in the oropharyngeal sub-set of patients, those tumors were HPV(+) fared better than those with HPV(-) tumors. Furthermore, the risk of death increased significantly with each pack-year of tobacco smoking. Using recursive-partitioning analysis, patients were classified as having low-risk of death if they had HPV(+) tumors, smoking history of ≤ 10 pack year or equivalent, tumor stage $< T4$ and nodal stage $< N3$ (Ang KK et al, NEJM 2010;363:24-35). In this protocol we will select patients with oropharynx cancer (OP) cancer who are at low risk according to these criteria for reduced treatment intensity, using RT concurrent with cetuximab instead of chemotherapy. This therapy will be compared to our experience in the past

few years using full dose chemo-RT, and will use the same detailed measures of toxicity, specifically measures of dysphagia, for comparison.

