2.0 STUDY HYPOTHESIS AND RATIONALE

Taking into account the excellent prognosis of patients with HPV-positive oropharyngeal cancer with ≤ 10 pack-year smoking, we hypothesize that reducing the intensity of therapy for these patients will reduce treatment sequelae, notably long-term dysphagia, without affecting their cure rates. The main Aim is to assess whether reducing treatment intensity, by replacing concurrent chemotherapy with cetuximab, will indeed achieve improved long-term toxicity. This Aim will be tested in a prospective study in which acute and long-term sequelae will be graded by observers (using CTCAE v4.0) and by patients (via HN-specific QOL questionnaires). Dysphagia will also be assessed objectively by videofluoroscopy. These measures will be compared to our historical control group (consisting of non-smoking patients with advanced oropharyngeal cancer who received standard-intensity chemo-RT and were evaluated by the same tools on UMCC protocol 2-21). Strict stopping rules will be enacted to ensure that reducing treatment intensity does not increase tumor failures compared with our previous results using standard therapy.

EGFR expression and down-stream signaling will be tested before and after the loading dose of cetuximab (before radiotherapy starts). We hypothesize that in this population with good prognosis, EGFR downstream inhibition after cetuximab test dose will be achieved in the large majority of patients, and that these characteristics will differ significantly from the characteristics of EGFR inhibition which will be observed in poor-prognosis oropharyngeal patients who smoke and/or have HPV- tumors. (These patients will be treated on a different, parallel protocol in which the intensity of therapy will be increased and in whom EGFR level will also be examined before and after a loading dose of cetuximab.)

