3.0 OBJECTIVES

3.1 Primary Objectives

- 3.1.1 To confirm that reducing treatment intensity in patients with HPV related oropharyngeal cancer and ≤ 10 pack-year smoking history by replacing concurrent chemotherapy with concurrent cetuximab, does not significantly increase the proportion of patients whose tumors recur, compared to our previous experience in similar patients receiving chemo-RT.
- 3.1.2 To compare the toxicity in patients receiving cetuximab-RT to similar patients treated with 7 weeks of chemotherapy concurrent with RT ("standard therapy") in UMCC 2-21.

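### As written, the primary recurrence index leaves out regional (nodal) recurrence; separately, the two events behind the stopping rule's 2/32 benchmark should be itemised

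*Combined protocol and SAP*

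**What the plan says.** **Primary index.** Section 20.3.1.1 states: "The primary index of recurrence will be the proportion of patients who have local recurrence, distant metastases or second primaries", counted within two years of the end of treatment. The null that this proportion exceeds 0.20 is tested by an exact binomial test at α=0.20. The objective it serves (3.1.1) is that de-intensified treatment "does not significantly increase the proportion of patients whose tumors recur". The Introduction describes the institution's earlier results in local-regional terms: "Taking into account the high local-regional control rates achieved in our oropharyngeal cancer patients".

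**Stopping rule.** Section 20.2 uses a different event: "Failure is defined as local-regional recurrence or metastasis, but not second primary cancer". Its historical rate is given as "2/32=6% of patients similar to those who will be treated in the current trial did not achieve tumor control". The rule stops accrual when the posterior probability that the failure rate "exceeded 0.1625 (0.1 more than the historical rate) is at least 0.75". The two historical events are not listed. Section 2.0 leans on this rule: "Strict stopping rules will be enacted to ensure that reducing treatment intensity does not increase tumor failures".

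**Historical events described elsewhere.** For HPV-positive never-users of tobacco the Introduction reports that "only one patient had disease progression (DM) (1/32, 3%), and an additional patient had a second primary in the oral cavity". It then summarises the group as having a 6% risk of metastasis or second primary, no LR events, and 93% disease-specific survival. Section 20.4.2.1 reports, for 33 non-smoking HPV-positive patients in UMCC 2-21, one death from metastases, one second primary in the oral cavity, three disease-free deaths, and no other events.

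**The concern.** Two definitions need attention.

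1. The sentence that fixes the primary endpoint names local and distant failure and second primaries, but not failure in the neck nodes. Node-positive patients are eligible (4.1 excludes only N3 among nodal stages), and 9.2 provides for neck dissection for PET-positive nodes, so nodal failure is foreseeable. Read literally, a nodal-only recurrence would count toward stopping the trial but not toward the primary test. With so few events allowed, one uncounted recurrence can turn a failed test into a pass.

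2. The stopping threshold is the historical rate plus 0.1. If the historical rate counts a second primary while the rule does not, the two are on different definitions and the stated reason for 0.1625 does not hold.

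**Working it through.** **Part 1: how many events the primary test tolerates**

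Inputs: null proportion 0.20, exact binomial test, α=0.20 (20.3.1.1). The null is that the proportion is too high, so the p-value is the lower tail P(X ≤ x | n, 0.20). Section 20.1 enrols 43 patients to obtain 36 who complete radiation and have both biopsies, so both n=36 and n=43 are shown.

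| n | events | P(X ≤ x), p=0.20 | result at α=0.20 |
|---|---|---|---|
| 36 | 4 | 0.127 | pass |
| 36 | 5 | 0.246 | not pass |
| 43 | 5 | 0.115 | pass |
| 43 | 6 | 0.216 | not pass |

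If the full count is one above the cut-off and one of those patients has only a nodal recurrence, the literal wording reports a pass. The documents do not say what fraction of failures would be regional only, so the calculation stops here.

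**Part 2: the 2/32 benchmark**

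*The plan's own figures.* 2/32 = 0.0625, and 0.0625 + 0.10 = 0.1625, as stated. Table 1 is the smallest r at each look with P(θ > 0.1625 | Beta(a+r, b+n−r)) ≥ 0.75. The prior is not stated. Priors with mean 2/32 and weight a+b of 1 or 2 both return 2, 3, 4, 5, 6, 7 at 5, 10, …, 30 patients, which is Table 1. Exact stopping probabilities for those boundaries, with each outcome known at its look, are 0.046, 0.594, 0.912, 0.992 and 0.9997 at true rates 0.06, 0.2, 0.3, 0.4 and 0.5. Table 2 gives 0.05, 0.59, 0.91, 0.99 and 0.99. The plan's figures reproduce.

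*The described events on the rule's definition.*
- Metastasis only: 1/32 = 3.1%. The Introduction writes this event as 1/32, 3%.
- Metastasis plus second primary: 2/32 = 6.25%, matching the 6% in 20.2.

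From the events described, 2/32 is reached only by adding the second primary.

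*Consequence if that is what happened.* 1/32 + 0.10 = 0.03125 + 0.10 = 0.13125. Boundaries at that threshold, with priors centred at the historical rate and weight 1 or 2:

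| Patients | 5 | 10 | 15 | 20 | 25 | 30 |
|---|---|---|---|---|---|---|
| Table 1 (0.1625) | 2 | 3 | 4 | 5 | 6 | 7 |
| At 0.13125 | 2 | 3 | 4 | 5 | 5 | 6 |

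| True failure rate | P(stop), Table 1 | P(stop), 0.13125 |
|---|---|---|
| 0.06 | 0.046 | 0.052 |
| 0.10 | 0.146 | 0.182 |
| 0.20 | 0.594 | 0.692 |

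The size depends on the prior. Weight 0.5 also lowers the 20-patient row (P(stop) 0.72 at a true rate of 0.20), and Beta(0.5, 0.5) gives 0.79.

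**The case against.** **On the index.** The surrounding text points to an intended local-regional meaning: the objective speaks of recurrence without restricting the site, 20.2 says local-regional, and the three-part index mirrors the DM/LR/SP grouping in the Introduction. That stands as evidence that this is a slip. It does not settle how the endpoint would be scored, because 20.2 spells out local-regional immediately before a section that says only local.

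A reader might infer that the omission raises the chance of a favourable primary result by a known amount. The documents do not support that. A changed result needs a count one above the cut-off, a patient whose only event within two years is nodal, and a scorer who follows the literal text.

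**On the benchmark.** A reader might infer that 2/32 certainly includes a second primary and that 0.1625 is therefore wrong. The documents do not establish this, for three reasons.
- Section 20.2 describes both patients as failures of tumor control, an odd description of a second primary.
- The cohorts are not shown to be the same: 32 patients from UMCC 9921 and 2-21 in 20.2, against 33 from UMCC 2-21 in 20.4.2.1. The Introduction's group are never-users and no T4/N3 exclusion is stated for them.
- One cancer death in 33 would be a crude disease-specific survival of 32/33 = 97%, whereas the Introduction gives 93%. Censoring could explain the gap, and so could a second disease death.

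All three stand. Nor does Table 2 become wrong in either case, since it depends only on the boundaries and the assumed true rate.

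Counting second primaries in the primary index but not in the stopping rule is not an error in itself. The question is only whether the rule's benchmark uses the rule's own definition.

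**Conclusion.** The primary index is wrong as written. It omits regional recurrence, which the objective and the stopping rule both cover. It is probably a slip, but it sits in the sentence that defines the primary test, where one event separates pass from fail (4 against 5 at n=36; 5 against 6 at n=43). No change in the probability of passing is claimed.

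The benchmark is a minor point for clarification, not a demonstrated design defect. The described events suggest that one of the two is a second primary, but a second true failure cannot be excluded. If one is a second primary, the effect is modest under weak priors of weight 1 or 2 centred at the historical rate: two late boundaries fall by one failure each, and P(stop) at a true rate of 0.20 goes from 0.59 to 0.69. Those figures assume immediately known outcomes and a prior that the plan does not state.

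**What to change.** **Section 20.3.1.1.** Define the index as *local, regional or distant recurrence, or second primary*. Leave second primaries and the 0.20 null as they are. Cost: a small wording change, with no effect on sample size or test.

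**Section 20.2.** Add one sentence itemising the two historical events under the rule's own failure definition.
- If both are failures of tumor control, document the second and keep 0.1625.
- If one is a second primary, choose one of two courses:
  - (a) Restate the rate as 1/32 and the threshold as about 0.131, state the prior, re-run the boundary program and reissue Tables 1 and 2. The price is more stopping of an acceptable regimen: P(stop) at a true rate of 0.10 rises from 0.146 to 0.182 under the priors above. It may also tie the rule to a group with less tobacco exposure than the one enrolled.
  - (b) Keep 0.1625 and replace its stated derivation with the actual justification. One candidate is that 4.3 admits patients with some smoking history, while the described events come from never-users or non-smokers. Cost: one further sentence, with no boundary changed.
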